1.5.1. The Biofilm Question

Colonization of the nephrostomy catheter occurs as soon as it is passed into the patient¹⁹, leading to the development of a three-dimensional biofilm²⁸, containing a high concentration of microorganisms which are under relative protection from both the immune system and antimicrobials, associated with intraluminal fouling can lead to catheter dysfunction and clinical infection, from pyelonephritis and abscesses to bacteremia and septic shock^{18, (29)}.

Biofilm is therefore a reservoir of microorganisms which can perpetuate an episode of infection or even facilitate a new one¹⁹. Therefore, the best way to prevent infection is to use the nephrostomy catheter for as short a time as possible. However, if patients need this catheter for a long period of time, one way of mitigating catheter-related urinary tract infection would be to change the catheter after a period of use.

The time used to change the catheter varies according to expert opinion and institutional protocols, ranging from 10 weeks³⁰ to 3 months³. One study proposed a model to define the best time to change, associated with fewer complications, better patient compliance and lower costs, concluding that changes could be made every 60 days⁽²⁰⁾.

In situations where urinary tract infections related to the nephrostomy catheter recur, a retrospective study suggests that the catheter should be changed up to four

(4) days after starting the appropriate antimicrobial to treat the current infection and maintain this antimicrobial for 14 days of treatment ⁽¹⁹⁾.

1.5.2. The question of antibiotics

Antibiotic prophylaxis in surgical procedures follows certain principles:

It is a brief administration of antibiotics before or at the beginning of an intervention used to minimize infectious complications related to diagnostic or therapeutic intervention. Even though its use is widely accepted, there are risks of side effects and the development of multidrug-resistant microorganisms ^{31, (32)}.

The potential benefit is determined by three conditions: patient-related factors (ability of the host to respond to bacterial invasion); procedure-related factors (likelihood of bacterial invasion at the surgical site) and the potential morbidity of the infection ⁽³²⁾.

It is only recommended when the potential benefits exceed the premeditated costs and risks ⁽³²⁾.

The antimicrobial agent used must be effective against the bacterial microorganism characteristic of the surgical site relevant to causing infectious disease, also considering the cost, convenience and safety of the antibiotic ⁽³²⁾.

Its duration should be for the period in which bacterial invasion is facilitated and/or likely to establish an infection ⁽³²⁾.

According to the *American Heart Association*, antimicrobials are no longer recommended in genitourinary procedures solely to prevent infective endocarditis as this is not an effective strategy. Infective endocarditis occurs as a result of random bacteremia associated with daily activities and not due to genitourinary procedures ^{32, (33)}.

However, it is only indicated against α -hemolytic streptococci in patients at high risk of developing infective endocarditis (patients with valve prostheses, previous history of infective endocarditis, congenital heart disease treated with material considered to be a foreign body or heart transplant with valvulopathy) and the use of amoxicillin or cefazolin is recommended ^{33, (34)}.

Based on these principles, antibiotic prophylaxis in urological procedures is an important and easily modifiable preventive measure to reduce postoperative infections. The decision to carry it out and the selection and dose of the antibiotic to be used can

be based on consensus, but a comprehensive assessment of the patient's specific circumstances should also be considered ⁽³²⁾.

Thus, specifically with regard to percutaneous nephrostomy, in some situations antibiotic prophylaxis may not be carried out, as suggested by a 1991 study, in patients at low risk of sepsis related to the procedure (14% of sepsis in those patients who were not given antibiotic prophylaxis and 10% of sepsis in those who received antibiotic prophylaxis, $p = 0.75$). However, for patients considered to be at high risk of urinary focus sepsis after the procedure (the elderly, those with diabetes *mellitus*, those with bladder dysfunction, patients using a delayed bladder catheter, patients who had undergone previous manipulation of the urinary tract, patients with uretero-intestinal anastomosis, stones and bacteriuria) the same study found that in patients who did not receive antibiotic prophylaxis the sepsis rate was 50% and in those who received antibiotic prophylaxis the sepsis rate was 9%, $p = 0.03$ ²². This study evaluated malignant and benign ureteral obstructions, mainly caused by calculi, and 12/56 (21.4%) of the patients developed signs of sepsis after percutaneous nephrostomy, but 9 of them had ureteral calculi and in 7 of these 12 patients percutaneous nephrostomy was used as an access for percutaneous nephrolithotomy ⁽²²⁾.

It is important to note that the proportion of sepsis in this study is high due to a possible latent ureteral infection secondary to the presence of calculi, which may be an important selection bias, and thus it is not possible to compare these high sepsis rates with other clinical situations requiring percutaneous nephrostomy catheters ^{22, 35}. The population of patients undergoing percutaneous nephrolithotomy with latent infections secondary to calculous disease is different from populations without calculi because the infection, even if latent, in the former is prior to the procedure, and it is not possible to attribute any sign of infection to the decompression performed by percutaneous nephrostomy and then judge it as a life-threatening procedure ⁽³⁵⁾.

In addition to the facts described above, the results of a 1989 study found the presence of bacteria in blood samples by collecting blood cultures before and after changing nephrostomy catheters used for long periods (not specifying the cause of ureteral obstruction) and evaluating the patients up to 24 hours after the procedures. None of them showed signs of infection and there were 11% of positive blood cultures (in 104 catheter changes) for patients who did and did not receive antibiotic prophylaxis ⁽³⁰⁾.

Formatado: Inglês (Estados Unidos)

Formatado: Inglês (Estados Unidos)

Código de campo alterado

Código de campo alterado

Formatado: Inglês (Estados Unidos)

In addition, Maneevase *et al.* in a retrospective study showed that diabetes, ileal conduit, chronic kidney disease, ureteral catheter, previous history of urinary tract infection and neutropenia were not considered risk factors for urinary tract infection related to percutaneous nephrostomy catheter in 216 procedures, however, they do not mention whether the first procedure for urinary tract clearance or its subsequent changes were studied ⁽³⁶⁾.

These older studies are the main references for drawing up some consensuses.

1.5.2.1. Urology consensus

Antibiotic prophylaxis is well established for transurethral resections of the prostate and prostate biopsies, but some systematic reviews and consensuses do not include percutaneous nephrostomy and make no mention of patients with neoplasms ^{31, (32)}.

In a review, the procedure evaluated that comes closest to percutaneous nephrostomy is percutaneous nephrolithotomy (removal of calculi, usually larger ones, directly through the obstructed kidney). Although calculous disease is benign, it can in itself be a hotbed of microorganisms, increasing the risk of urinary tract infections after percutaneous nephrolithotomy. Therefore, antibiotic prophylaxis is recommended for all procedures. Even so, when the preoperative uroculture is negative, there is little evidence to suggest a more favorable result in the prevention of urinary tract infection after percutaneous nephrolithotomy when antibiotic prophylaxis is carried out, without a clear advantage with any specific antimicrobial regimen used ⁽³¹⁾.

The second review also does not include percutaneous nephrostomy in its analysis of antibiotic prophylaxis in urological procedures, but the closest procedure evaluated is percutaneous renal surgery, and prophylaxis is indicated in all patients, but with level of evidence IIb (evidence obtained from at least one or other type of well-designed quasi-experimental study) and III (evidence obtained from well-designed non-experimental studies - comparative studies, correlation studies and case reports). Nor does it mention prophylaxis in percutaneous procedures with long-term catheters or catheter changes ⁽³²⁾.

An important study evaluating various regions of the world on the use of antibiotics in urological procedures observed that 50% of the use of antimicrobials was for prophylaxis and that 75% of the use of all antimicrobials was empirical in nature. They conclude that there are significant differences between countries, regions and

types of hospital in the use of antibiotic prophylaxis, especially for clean procedures and the type of antibiotic used (the most common were ciprofloxacin and cephalosporins in general), which are not always consistent with evidence-based consensus⁽³⁷⁾.

More recent urological consensus continue to recommend the use of antibiotic prophylaxis with cefazolin associated with aminoglycoside if there is manipulation of the urinary tract or implantation of prostheses in procedures considered clean-contaminated, but none of them mention percutaneous nephrostomy itself⁽³⁸⁻⁴¹⁾.

1.5.2.2. Interventional radiology consensus

The consensus on antibiotic prophylaxis in procedures performed by interventional radiologists are the ones that most often mention percutaneous nephrostomy. These documents also define colonization as the presence of a microorganism without leading to a systemic inflammatory response^{34, (42)}.

They recommend the use of antibiotic prophylaxis for all patients, except for catheter changes in non-infected cases, without obstruction and in immunocompetent patients because there is no description in the literature, but also, without guarantees, with levels of evidence ranging from historical, non-randomized or case-control studies to case series without control group, with limited data and expert opinions (grade of recommendation IIb, with level of evidence in limited data and expert opinion)^{34, (42)}.

Brick *et al.* retrospectively evaluated 493 percutaneous nephrostomy catheter exchange procedures carried out on 126 patients, 213 procedures before a change in clinical practice and 280 procedures after this change which consisted of not carrying out antibiotic prophylaxis on patients considered to be at low risk of infection, as suggested by the consensus described above. High risk was considered to be the presence of 2 to 5 risk factors and low risk 0 to 1 of these factors, which were type II diabetes, previous urinary tract infection, history of neoplasm or obstruction, hypertension and kidney transplantation. Using the risk stratification model used, the authors concluded that changing the prophylaxis practice used had no effect on the rate of hospital admission due to infection or on the rate of infection in outpatients, corroborating that not using antibiotic prophylaxis for routine catheter changes in patients at low risk of infection does not increase the rate of infection⁽²⁷⁾.

1.5.2.3. Antibiotic prophylaxis for percutaneous nephrostomy in cancer patients

Few studies have evaluated this issue in the context of percutaneous nephrostomy and malignant ureteral obstruction. One of them evaluated the role of antibiotic prophylaxis in urological procedures, with percutaneous nephrostomy performed in 15.3% of patients with both benign and malignant ureteral obstruction. The patients were followed up for 30 days after the procedure, and the only event studied was the presence of fever²⁶. Antibiotic prophylaxis was carried out in two ways, in the first group 30 minutes before the procedure and in the second group immediately after the procedure. Feverish complications occurred in 4.5% of both groups and in all procedures (ureteral catheters, nephrostomy and retrograde pyelography), with no statistical difference. The authors found that pyuria before the procedures and the degree of hydronephrosis were risk factors for urinary infection, and that antibiotic prophylaxis may be more beneficial in these situations⁽²⁶⁾.

Another retrospective study evaluated antibiotic prophylaxis and urinary infection after the first nephrostomy catheter passages for urinary tract clearance and after catheter changes in the oncology population. Fifty-one percent of the patients studied underwent nephrostomy catheter replacement. Patients were followed up for 90 days and 19% had catheter-related pyelonephritis and 7.5% had asymptomatic bacteriuria after the first passage³. Half of the patients who had pyelonephritis developed the infection one month after catheter insertion. Of the patients who had their catheters changed, 4% developed pyelonephritis and 2% asymptomatic bacteriuria. The authors concluded that the rate of pyelonephritis related to nephrostomy catheter insertion is relatively high, mainly due to gram-positive germs, with previous urinary tract infection and neutropenia being the main risk factors. The authors also concluded that antibiotic prophylaxis does not prevent nephrostomy catheter-related pyelonephritis, suggesting that the main risk factor for this infection is simply the existence of tumor disease⁽³⁾.

A retrospective cohort carried out at this institution evaluated 180 percutaneous nephrostomies (87 first passes and 93 catheter changes) over a 3-year period. The occurrence of urinary tract infection related to the nephrostomy catheter was verified up to 7 days after the procedures, with 1.2% of urinary tract infection related to the nephrostomy catheter being identified after its first passage and 11.4% after catheter changes ($p = 0.01$)⁴³. In the first passages, there was no statistically significant difference in urinary infection rates when the patient received antibiotic prophylaxis or

not (0% *versus* 1.5%, respectively; $p = 0.999$). In catheter changes, even without statistical significance ($p = 0.146$), the urinary infection rate was 21.4% in those patients who did not receive antibiotic prophylaxis; 14.8% in those who received empirical antibiotic prophylaxis and 6.4% in those who received targeted antibiotic prophylaxis (with antibiotics guided by a previously collected uroculture result)⁴³. Despite the potential bias in results due to its retrospective nature, this study demonstrates a reality in clinical practice and also a possible solution both to prevent urinary infections in this population and to help rationalize the use of antibiotics.

Finally, a prospective study assessed the incidence of urinary tract infection after nephrostomy catheter changes without antibiotic prophylaxis and found that out of 126 catheter change procedures, 13.5% had infectious complications. Just over half (52.9%) required antibiotic treatment and only 1 patient was hospitalized for such treatment, but without threatening the patient's life, according to the authors⁽⁴⁴⁾.

Consequently, there are more doubts than certainties about antibiotic prophylaxis in percutaneous nephrostomy in cancer patients.

Based on what has been said so far, two fundamental questions can be posed. Firstly: would it be necessary to carry out antibiotic prophylaxis for the first passage of the percutaneous nephrostomy catheter to prevent urinary infection related to the procedure? And secondly: can uroculture-guided antibiotic prophylaxis be superior in preventing urinary tract infection when compared to empirical antibiotic prophylaxis after percutaneous nephrostomy catheter changes guided by imaging? These are the questions that guide this research project.

2.

- a) There is no consistent data in the literature to answer whether the use of antibiotic prophylaxis before nephrostomy helps prevent urinary tract infection in cancer patients;
- b) There is not enough data in the literature to define the best antibiotic prophylaxis approach (prophylactic or uroculture-guided) for catheter changes in cancer patients;
- c) There are no clinical trials on antibiotic prophylaxis in percutaneous nephrostomy, probably because it is difficult to perform even for ethical reasons, especially in patients with advanced cancer.
- d) Nor are there any systematic reviews or meta-analyses on this subject.
- e) Much of the existing literature is made up of heterogeneous studies that are not specific to the cancer population and whose results are applied in a generalized and inaccurate way, such as the irrational use of antibiotics.
- f) Consensus on antibiotic prophylaxis in urological procedures does not mention percutaneous nephrostomy.

3. OBJECTIVES

3.1. Primary

- To evaluate the rate of urinary tract infection related to the percutaneous nephrostomy procedure in cancer patients, according to the use of antibiotic prophylaxis at the first catheter passage and subsequent changes, a retrospective cohort and systematic review with meta-analysis will be conducted.

3.2. Secondary

- Describe the frequency of urinary tract infection related to the percutaneous nephrostomy catheter that occurs between catheter changes (not related to the procedure, but possibly to colonization of the catheter);
- To describe and compare the results of the urocultures involved in the study, as well as their sensitivity to the antibiotics used;
- Describe the main signs and symptoms involved in urinary tract infection related to the procedure and the nephrostomy catheter;

- Assess the severity of urinary tract infections according to the type of treatment and the need for hospitalization.
- To determine the risk factors for urinary tract infection related to the passage and subsequent changes of nephrostomy catheters.
- Describe the rates of urinary infections and associated germs according to the time of nephrostomy passage, first passage or catheter change.
- Report whether these catheters were changed when the urinary tract infection occurred and on which day after the urinary tract infection was diagnosed.

4. MATERIAL AND METHODS

4.1. Study design

Hybrid design: Retrospective cohort study with systematic review and meta-analysis.

4.2. Study site

This study will be carried out in the interventional radiology department of two Pio XII Foundation hospitals (Barretos Cancer Hospital and Jales Cancer Hospital).

4.3. Factor under study

The factor under study will be antibiotic prophylaxis.

4.4. Outcome

The outcome will be urinary tract infection.

4.5. Breakdown of the methodology

This section is divided into parts I, II and III for a better understanding of the design and conduct of the study.

Part I - Retrospective Cohort Study

4.6. Inclusion criteria

- Patients with neoplasms being followed up at the Pio XII Foundation.
- Progression with malignant ureteral obstruction and need for clearance.
- Patients undergoing percutaneous nephrostomy to clear the urinary tract and for subsequent nephrostomy catheter changes.

4.7. Exclusion criteria

- Use of percutaneous nephrostomy for other procedures such as passage of a double-J catheter via the antegrade route.
- Use of percutaneous nephrostomy to treat clinical conditions other than malignant ureteral obstruction, such as stenosis secondary to Bricker's ileal conduit.
- Use of percutaneous nephrostomy to clear the urinary tract of non-neoplastic causes, such as stones or non-malignant stenosis.
- Use of antibiotics to treat urinary tract infection when performing percutaneous nephrostomy (first pass or exchange).
- Patients on suppressive antibiotic therapy.

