4.10.1. Definitions

In order to carry out this study, it is necessary to establish some concepts, some of which are not yet standardized in the medical literature:

- **Urinary tract colonization:** occurs when there is a positive uroculture result (presence of infectious agents such as bacteria or fungi) in the absence of clinical signs suggestive of infection. In these cases, antibiotic treatment is not necessary (45).
- **Urinary tract infection:** occurs when there are signs and symptoms suggestive of local infection, such as cystitis (bladder infection or lower urinary tract infection) or pyelonephritis (kidney infection or upper urinary tract infection) associated with a positive uroculture result, requiring treatment with antibiotics ^{3, 19, (46)}.

- **Urinary tract infection related to the percutaneous nephrostomy procedure:** when the urinary tract infection occurs shortly after the procedure has been carried out, in this case, percutaneous nephrostomy (first pass or catheter changes).
- **Urinary tract infection related to the nephrostomy catheter:** when the urinary tract infection occurs at another time unrelated to the procedure and in the presence of the nephrostomy catheter and in the absence of another focus justifying the infection.

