4.10.2. First pass procedure

This group will be made up of patients who have undergone percutaneous nephrostomy for urinary tract clearance and we will study whether or not antibiotic prophylaxis was recorded in the medical records to be reviewed at these hospitals.

The following laboratory tests will be considered: serum creatinine and urea levels, urine samples for tests such as urine summary (or type I urine) and uroculture with antibiogram.

The proportion of urinary tract infections that developed within 7 days of the procedure will be studied. A procedure-related urinary tract infection is considered to be any report in the medical record of clinical signs and symptoms associated with uroculture results (see definition in item 4.10.4.) and the location of the respective treatment will be documented: outpatient, inpatient or intensive care unit (ICU).

It will be documented whether there is evidence reported in medical records of urinary tract infections or the presence of bladder fistulas prior to the procedure.

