4.10.3. Procedure for changing the catheter

Catheter changes take place electively approximately every 90 days after the previous procedure (first pass or previous catheter change), scheduled during outpatient follow-up. However, this change can happen earlier than planned due to situations such as catheter obstruction and migration, or even catheter-related urinary tract infection.

This group will be made up of patients undergoing percutaneous nephrostomy catheter exchange and will study the use of empirical or targeted antibiotic prophylaxis documented in medical records to be reviewed at the two hospitals.

The Jales Cancer Hospital will study targeted antibiotic prophylaxis, which consists of collecting the following laboratory tests around 7 days before the procedure

to change the nephrostomy catheter(s) to guide the antibiotic to be used for prophylaxis: serum creatinine and urea levels, urine samples for tests such as urine summary (or type I urine) and uroculture with antibiogram. If the tests are not carried out prior to the procedure or if the uroculture does not show a specific bacterial agent, the procedure will be studied according to empirical antibiotic prophylaxis.

The Hospital de Câncer de Barretos will study the empirical antibiotic prophylaxis carried out according to daily clinical practice, recorded in the medical records to be reviewed of patients undergoing percutaneous nephrostomy catheter exchange.

The proportion of urinary tract infections that developed within 7 days of the procedure will be studied. A procedure-related urinary tract infection is considered to be any report in the medical record of clinical signs and symptoms associated with uroculture results (see definition in item 4.10.4.) and the location of the respective treatment will be documented: outpatient, inpatient or intensive care unit (ICU).

It will be documented whether there is evidence reported in medical records of urinary tract infections or the presence of bladder fistulas prior to the procedure.

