4.10.4. Urinary tract infection

A urinary tract infection will be considered to be the presence of clinical signs and symptoms suggestive of infection, such as fever (axillary temperature greater than 37.8°C), chills, low back pain, pain at the wrist-percussion of the lumbar region and/or the presence of cloudy urine in the collection bag, plus a uroculture with the presence of microorganisms (no more than two) with more than 100,000 CFU/ml.

If the urinary tract infection is diagnosed 7 (seven) days after the procedure (first catheter passage or change), it will be considered a procedure-related urinary tract infection.

If a urinary tract infection is diagnosed between catheter changes, it will be considered a catheter-related urinary tract infection.

The laboratory tests to be studied will be blood count, creatinine and urea, C-reactive protein, type I urine, uroculture and antibiogram and samples of blood cultures and antibiograms collected at the time of diagnosis of the urinary tract infection.

If the participant receives treatment for a possible urinary tract infection occurred between catheter changes at another service, it will be considered an infection if there is an improvement in the symptoms reported by the participant in the medical records and the antimicrobial used for the treatment will be verified.

The antibiotic(s) used for treatment will be duly studied and registered

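### The infection exclusion is triggered by antibiotic treatment and the outcome is dated by diagnosis, so an untreated infection already present at the procedure can be counted as procedure-related

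*Protocol*

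**What the plan says.** **Eligibility.** Protocol section 4.7 lists "Use of antibiotics to treat urinary tract infection when performing percutaneous nephrostomy (first pass or exchange" as an exclusion, and separately "Patients on suppressive antibiotic therapy". Both depend on an antibiotic being given. Nothing in 4.6 or 4.7 refers to symptoms, a urine culture, or infection as such at the time of the procedure.

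**Prior infection.** Section 4.10.2 says of earlier infection: "It will be documented whether there is evidence reported in medical records of urinary tract infections". Section 4.10.3 repeats this for catheter changes. Neither section uses the information for eligibility or for classifying the outcome. Section 4.10.3 also says of the roughly 90-day change that "this change can happen earlier than planned due to situations such as catheter obstruction and migration, or even catheter-related urinary tract infection".

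**Outcome.** Section 4.10.1 describes a procedure-related UTI as one "when the urinary tract infection occurs shortly after the procedure has been carried out". Section 4.10.2 states: "The proportion of urinary tract infections that developed within 7 days of the procedure will be studied". Both then rely on the working definition in 4.10.4, which combines signs or symptoms with a positive culture and attributes the event to the procedure "If the urinary tract infection is diagnosed 7 (seven) days after the procedure". I read this as diagnosis within 7 days, in line with 4.10.2.

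**Comparisons.** Section 4.12 compares prophylaxis with no prophylaxis at first passage, and empirical with targeted prophylaxis at catheter changes. The SAP leaves these rules unchanged.

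**The concern.** A patient may have fever or flank pain when the catheter is placed and be on no treatment, with the culture result still to come. Section 4.7 does not remove that procedure. If the culture is positive three days later, the episode meets 4.10.4 and is dated inside the window. It then counts as caused by a procedure that it preceded.

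The protocol recognises this problem elsewhere. In section 1.5.2 it discounts a stone-disease series because, where infection comes first, "it is not possible to attribute any sign of infection to the decompression performed by percutaneous nephrostomy".

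There is a second difficulty. Whether an infected patient stays in the study depends on whether an antibiotic was given and how it was labelled. An infected patient whose antibiotic is recorded as treatment leaves the study. If the dose is recorded as prophylaxis, the patient stays in a prophylaxis group. With no antibiotic at first passage, the patient stays in the no-prophylaxis group. Selection is thus tied to the factor under study (section 4.3), and the groups need not be affected equally. At stake is whether the primary outcome measures infection that follows the procedure, and whether group differences in it can be interpreted.

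**Working it through.** **1. Reading the rules together.**

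| Infection present at the procedure | Removed by 4.7? | Can it meet 4.10.4 within 7 days? |
|---|---|---|
| Recognised, antibiotic recorded as treatment | Yes | Not applicable |
| Symptoms present, culture pending, no antibiotic | No | Yes, once the culture is reported |
| Symptoms present, dose recorded as prophylaxis | No | Yes |
| Unrecognised at the time | No | Yes, if diagnosed in the window |

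The last three rows are the gap. The documents do not say how often they occur.

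**2. Inputs from the documents.**
- Section 4.9 gives 372 first passes and 358 changes: 372 + 358 = 730, which agrees with the stated total. It is a convenience count, with no target effect or power.
- Section 1.5.2.3 describes the institution's earlier cohort: 87 first passes, with 7-day UTI of 1.2% overall, 1.5% without prophylaxis and 0% with it.
- Section 4.12 sets a two-sided 5% level, with chi-square or Fisher tests.

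**3. Assumed split.** One event at 1.5% fits a denominator of 65 to 68; I take 66 of 87.
- Without prophylaxis: 66/87 × 372 = 282.
- With prophylaxis: 372 − 282 = 90.
- Starting events without prophylaxis: 1.5% × 282 ≈ 4, against 0 of 90.

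**4. Adding misattributed infections (two-sided Fisher test).** The numbers added are illustrative.

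| Added, no prophylaxis | Added, prophylaxis | Events /282 | Events /90 | p |
|---|---|---|---|---|
| 0 | 0 | 4 (1.4%) | 0 | 0.58 |
| 3 | 0 | 7 (2.5%) | 0 | 0.20 |
| 6 | 0 | 10 (3.5%) | 0 | 0.13 |
| 9 | 0 | 13 (4.6%) | 0 | 0.044 |
| 9 | 1 | 13 (4.6%) | 1 (1.1%) | 0.20 |
| 0 | 6 | 4 (1.4%) | 6 (6.7%) | 0.015 |

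One event in the prophylaxis group moves 0.044 to 0.20. Six events there reverse the finding.

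**5. Chance of a false significant result.** Take a new-onset rate of 1.2% in both groups (no prophylaxis effect) and a proportion q of counted pre-existing infection. The observed rate is q + (1 − q) × 0.012; for q = 5% this is 0.05 + 0.95 × 0.012 = 6.1%. Exact enumeration of the Fisher test over 372 procedures gives:

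| q, no prophylaxis | q, prophylaxis | 186/186 split | 279/93 split |
|---|---|---|---|
| 0 | 0 | 0.6% | 2.3% |
| 2% | 0 | 14% | 6% |
| 5% | 0 | 65% | 45% |
| 10% | 0 | 99% | 95% |
| 5% | 5% | 3.0% | 3.5% |
| 0 | 5% | 65% (reversed) | 68% (reversed) |

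Every q and both splits are assumptions. Even contamination does not create a difference; it dilutes a real one.

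**The case against.** The strongest reply is that the plan already intends new onset. Sections 4.10.1 to 4.10.3 speak of infections that arise or develop after the procedure. Section 4.10.1 also describes UTI as needing antibiotics, so a recognised case would usually be on treatment and excluded. A UTI that prompts an early change was noticed before that change; 4.10.3 itself calls it catheter-related, and 4.10.4 puts infections diagnosed between changes in that category. Prior UTI is recorded and could enter the logistic model if it passes the p < 0.20 screen. The stone-disease argument in 1.5.2 concerns latent infection from calculi, and 4.7 excludes stones.

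Much of this stands. It narrows the gap to unrecognised, culture-pending or mislabelled infection, and it means an existing infection could count, not that it will. The stone-disease passage supports the principle but does not concern this population. The reply does not close the gap: stated intent gives a record abstractor no rule, the definition actually applied goes by diagnosis date, and screening on a p-value does not correct a misclassified outcome.

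A reader might infer that the error falls mainly on the no-prophylaxis group and so creates an apparent benefit of prophylaxis. The documents do not support that. An infected patient whose dose is recorded as prophylaxis stays in a prophylaxis group with an event, which pushes the other way. The 358 catheter changes have no planned no-prophylaxis group at all.

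**Conclusion.** The point holds as a defect in how eligibility and outcome fit together: the rules as written let an infection that precedes the procedure count as a primary event, and they select on antibiotic use. The direction and size of any bias cannot be derived from the documents, which give neither the prevalence of untreated infection nor its split between groups. The earlier cohort's 1.5% may itself include such cases, since its handling of existing infection is not described.

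The calculations show sensitivity only. At a first-pass rate near 1.2%, about 4 events are expected in 372 procedures (372 × 0.012 = 4.5), so a handful of misattributed events in one group could produce, remove or reverse a significant result. This rests on the assumed 282/90 split and illustrative counts. For catheter changes the same misclassification can affect the empirical-versus-targeted comparison; I have not sized it. The rules should be tightened before the primary result is interpreted.

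**What to change.** 1. **Outcome (4.10.4).** Count a UTI as procedure-related only if the qualifying signs or symptoms are first recorded after the procedure and within 7 days.
2. **Primary comparison (4.7 or 4.12).** Exclude procedures with an active, unresolved episode, whether or not antibiotics were given. Define this as qualifying signs or symptoms recorded at the procedure or in a fixed short window before it, or UTI recorded as the reason for the procedure. The window could be the 7 days or so in which 4.10.3 places the pre-change tests. It needs a lower limit, since otherwise any past episode would exclude.
3. **Reporting.** Give the result with and without these procedures, and tabulate pre-procedure UTI by group. Keep the excluded changes for the section 3.2 objective on catheters changed when infection occurred.

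These changes concern classification and analysis only. The SAP is written in the past tense, so they can be applied as a re-analysis or sensitivity analysis.

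The cost is a few sentences and some further record review. Section 4.10.5 lists the presence of symptoms but no onset date, so timing relative to the procedure must be abstracted, and some records may not show it. The number of procedures that leave the primary comparison is not known in advance.
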